### Amendment 2.0 (11 Oct 2022)

Change	Rationale	Section(s) affected
Changed the sponsor contact from PPD to PPD.	[name] is the new clinical science lead for the gbt021601-022 study.	Title page Statement of approval and signature
Increased the frequency of study visits for participants rolling into the gbt021601-022 study from the gbt021601-012 study.	Due to quality issues at the site of the gbt021601-012 study, additional visits and assessments for these participants rolling into the open label extension study from the gbt021601-012 study were included to closely monitor the safety and pk of the participants.	Section 1.1 Section 1.2 Section 2.2 Section 2.3 Section 4.1 Section 4.3 Section 8.2 Appendix 1 – table 12
Updated the test product information from gbt021601 may be provided as a coated dispersible tablet to “an appropriate oral formulation for pediatric participants who cannot swallow the regular tablet”	The pediatric formulation is still being developed.	Section 1.1 Section 6.1
Revised the serious adverse event reporting from paper forms to the electronic case report forms via the electronic data capture system.	All adverse event reporting should now be captured electronically to minimize error.	Section 8.4.6

### Amendment 1.0 (19 July 2022)

Change	Rationale	Section(s) affected
Revised the baseline visit to coincide with the day 1 visit and added clarification language to assessments done at that visit.	It is intended for the day 1 baseline visit to coincide with the final visit from the originating gbt021601 study.	Section 1.1 synopsis Section 1.2 schedule of assessments (table 1, table 2, table 3) Section 4.1 overall design

## 11.8. Appendix 6: Abbreviations

Abbreviation	Term
A1 to A3	albuminuria (KDIGO albuminuria severity standardization)
ACS	acute chest syndrome
AE	adverse event
AKI	acute kidney injury
ALT	alanine aminotransferase
aPTT	activated partial thromboplastin time
AST	aspartate aminotransferase
BID	twice daily
BSA	body surface area
CBD	cannabidiol
CGI-C	Clinical Global Impression of Change
CGI-S	Clinical Global Impression of Severity
CKD	Chronic Kidney Disease
CKD-EPI	Chronic Kidney Disease Epidemiology Collaboration
CRF	case report form
CRO	contract research organization
CSR	clinical study report
CT	clinical trial
CTCAE	Common Terminology Criteria for Adverse Events
CTIS	Clinical Trial Information System
CCI	
DDI	drug-drug interaction
DICI	drug-induced creatinine increase
DIKI	drug-induced kidney injury
DILI	drug-induced liver injury
DSM-V	Criteria for Substance Use Disorders
EC	Ethics Committee
ECC	Emergency Contact Card
eCrCl	estimated creatinine clearance
eCRF	electronic case report form
EDB	exposure during breastfeeding

Abbreviation	Term
EDP	exposure during pregnancy
eGFR	estimated glomerular filtration rate
EMEA	Europe, Middle East, and Africa
EOS	end of study
EOT	end of treatment
EPO	erythropoietin
ET	early termination
EU	European Union
EudraCT	European Union Drug Regulating Authorities Clinical Trials (European Clinical Trials Database)
FDA	Food and Drug Administration
FSH	follicle-stimulating hormone
GBT	Global Blood Therapeutics, Inc
GCP	Good Clinical Practice
h	hour
Hb	hemoglobin
HbS	sickle hemoglobin
HIV	human immunodeficiency virus
HRQOL	Health-related quality of life
HSCT	hematopoietic stem cell transplantation
Ht	height
HU	hydroxyurea
IB	Investigator's Brochure
ICE	Intercurrent events
ICF	informed consent form
ICH	International Council for Harmonisation of Technical Requirements for Pharmaceuticals for Human Use
ID	identification
IEC	Independent Ethics Committee
IgM	Immunoglobulin M
IND	Investigational New Drug
IMP	Investigational medicinal product

Abbreviation	Term
INR	International Normalized Ratio
IRB	Institutional Review Board
IRT	Interactive response technology
K	Proportionality constant
LDH	lactate dehydrogenase
LFT	liver function test
MAD	Multiple ascending dose
MOA	Mechanism of action
MQI	Medically Qualified Individual
NA	Not applicable
NCI CTCAE	National Cancer Institute Common Terminology Criteria for Adverse Events
NIRS	near infrared spectroscopy
NIMP/AxMP	Non Investigational Medicinal Product/Auxiliary Medicinal Product
NRS	numeric rating scale
NSAIDs	nonsteroidal anti-inflammatory drugs
CCI	
OLE	open-label extension
Oxy-Hb	Oxygen-hemoglobin
PACL	Protocol Administrative Change Letter
PD	pharmacodynamic
PE	Physical examination
PGI-C	Patient Global Impression of Change
PGI-S	Patient Global Impression of Severity
CCI	
PIP	Pediatric Investigation Plan
PK	pharmacokinetic
PPK	population pharmacokinetic
PRO	Patient-Reported Outcome
PROMIS	Patient-Reported Outcome Measurement Information System
PSP	Pediatric Study Plan
PSSA	Pfizer's Serious Adverse Event Submission Assistant
PT	prothrombin time

Abbreviation	Term
QD	once daily
QTLs	Quality tolerance limits
RBC	red blood cell
SAD	single ascending dose
SAE	serious adverse event
SAP	statistical analysis plan
SC	sickle cell
SCD	sickle cell disease
Screat	serum creatinine
Scys	serum cystatin C
SF	short form
SoA	schedule of assessments
SOC	Standard of care
SRSD	Single Reference Safety Document
SUSAR	suspected unexpected serious adverse reactions
$t_{1/2}$	Half-life
T bili	total bilirubin
TEAE	treatment-emergent adverse event
THC	tetrahydrocannabinol
$T_{max}$	time of maximum concentration
TME	targeted medical events
ULN	upper limit of normal
US	United States
VOC	vaso-occlusive crisis
WPAI+CIQ:SCD	Work Productivity and Activity Impairment plus Classroom Impairment Questionnaire: Sickle Cell Disease v2.0

### 1. VERSION HISTORY

**Table 1. Summary of Changes**

Version/ Date	Associated Protocol Amendment	Rationale	Specific Changes
1.0 / 23 Jun 2025	Protocol amendment 4.0 dated 06 Feb 2024	Not Applicable (N/A)	N/A

## 2. INTRODUCTION

This statistical analysis plan (SAP) provides the detailed methodology for summary and statistical analyses of the data collected in Study C5351005.

The primary analysis for this study will occur after all enrolled participants have completed End of Study (EOS) visit or have discontinued the study.

### 2.1. Modifications to the Analysis Plan Described in the Protocol

- All VOC data will be summarized including the events that occur after the inter-current events described in the protocol.
- All data for hemoglobin, reticulocytes, lactate dehydrogenase, and unconjugated bilirubin will be summarized including the data after the inter-current events described in the protocol.
- Updated definition of PK analysis set.
- Changed endpoint from “Incidence of SCD-related SAEs” to “Incidence of SCD-related AEs” to include all AEs.

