## 7.7. Concomitant Medications and Procedures

Study participants will be allowed to take other medications as needed except for those described in Section 11.6. Vaccines are allowed during the study. All concomitant medications will be documented.

In the interests of participant safety and acceptable standards of medical care, the Investigator will be permitted to prescribe treatment(s) at their discretion. Treatment with stable doses of

HU, L-glutamine are allowed. However, initiation of new SOC agents (eg, crizanlizumab and voxelotor) during treatment is strongly discouraged. All other standard therapeutic interventions for SCD and its complications (eg, hydration, analgesia, acute transfusions) are allowed under this protocol.

All concomitant treatments and/or procedures must be recorded in the participants' eCRF (procedure, medication, dose, treatment duration and indication).

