### 10.3.3. Secondary Endpoint(s)/Estimand(s) Analysis

Secondary Endpoints	Statistical Analysis Method

 
Annualized rate of VOC
 
	
Annualized rate of VOC will be summarized using descriptive statistics and a negative binomial model.
 
VOC data will be censored from the analysis after the following events:
 
 
New HU use post baseline;
 
Post baseline usage of prohibited/restricted medications known to affect Hb/VOC;
 
RBC exchange transfusion post baseline.
 

 
Incidence of SCD related SAEs
 
	
Descriptive statistics of SCD related SAEs will be provided.

 
Change from baseline in hematological laboratory parameters, including hemoglobin, reticulocytes, lactate dehydrogenase, and unconjugated bilirubin.
 
	
Change from baseline in hemoglobin, reticulocytes, lactate dehydrogenase, and unconjugated bilirubin will be summarized using descriptive statistics.
 
 
The following data will be excluded from the analysis: Data collected on or after the start of new HU use post baseline;
 
Data collected on or after the post baseline usage of prohibited/restricted medications known to affect Hb/VOC;
 
Data collected on or after start of post baseline RBC exchange transfusion;
 
Data collected from the start of post baseline RBC non-exchange transfusion for 18 weeks. (Data collected after the 18 weeks will be included in the analysis.)
 

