#### **6.2.2. Change from baseline in hematological laboratory parameters, including hemoglobin, reticulocytes, lactate dehydrogenase, and unconjugated bilirubin.**

Descriptive statistics (Section 5.3) for each parameter will be presented at baseline and each evaluation post baseline. Change from baseline for each post baseline evaluation will also be presented.

Mean (SD) for both raw values and change from baseline values will be plotted over time. These figures will be presented for each parameter separately.

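### The SAP drops the protocol's exclusions for transfusion, new hydroxyurea and other confounding drugs from the Hb, hemolysis and VOC analyses, gives no reason, and adds no supplementary summary or count of those affected

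*SAP*

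**What the plan says.** Protocol 10.3.3 sets two rules for the secondary endpoints.

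- **Laboratory parameters (Hb, reticulocytes, LDH, unconjugated bilirubin).** The excluded data begin with "Data collected on or after the start of new HU use post baseline". The same applies from the start of prohibited or restricted medication known to affect Hb or VOC, and from the start of exchange transfusion. For simple transfusion the exclusion is temporary: "Data collected from the start of post baseline RBC non-exchange transfusion for 18 weeks", after which data count again.
- **VOC.** "VOC data will be censored from the analysis after the following events": new HU, the same class of medications, and "RBC exchange transfusion post baseline". Simple transfusion is not on the VOC list.

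SAP 2.1 withdraws both rules. For the laboratory parameters: "All data for hemoglobin, reticulocytes, lactate dehydrogenase, and unconjugated bilirubin will be summarized including the data after the inter-current events described in the protocol". For VOC: "All VOC data will be summarized including the events that occur after the inter-current events described in the protocol". It states no reason. SAP 6.2.2 then plans only by-visit summaries: "Descriptive statistics (Section 5.3) for each parameter will be presented at baseline and each evaluation post baseline", plus change from baseline and mean plots. SAP 6.2.1 counts VOC person-time from first dose to end of treatment, without stopping at any of these events. SAP 2.2.2 gives the secondary estimand as not applicable, and SAP 6.4 plans no subset analyses.

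Protocol 7.7 permits acute transfusions during treatment.

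**The concern.** The four laboratory parameters serve the objective on the effect of long-term osivelotor on hemolytic anemia. The protocol treated all four as unfit for that purpose for 18 weeks after a simple transfusion, and permanently after new HU, the listed drugs or exchange transfusion. Under the SAP those values enter every visit mean. The study has no comparator (protocol 5.2), so no second arm absorbs the effect of co-treatment.

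A reader of the report would see one set of means and could not tell how many participants or visits followed a transfusion or a new therapy. The word transfusion does not appear in the SAP.

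The problem is sharpest for participants who roll over directly. By SAP Appendix 1.2, when the gap is under 7 days the baseline is the parent study's Week 12 value, taken on osivelotor. If the dose then stays the same, little further drug-related change is expected, and a modest transfusion effect could be a large part of what is displayed.

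**Working it through.** The plan gives no figure for this point, so there is none to reproduce. The check is a comparison of text, followed by sizing under stated assumptions.

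**1. The rules side by side**

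| Event | Protocol 10.3.3, laboratory | Protocol 10.3.3, VOC | SAP 2.1 |
|---|---|---|---|
| New HU | excluded from start | censored after | kept |
| Prohibited/restricted drugs known to affect Hb/VOC | excluded from use | censored after | kept |
| Exchange transfusion | excluded from start | censored after | kept |
| Simple transfusion | excluded for 18 weeks | no rule | kept |
| Stable HU, L-glutamine | no rule | no rule | kept (no change) |

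SAP 6.5.5 summarizes concomitant medications, which would show HU use. It does not separate new from continuing use and does not mention transfusion.

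**2. Visits touched by one simple transfusion** (schedules in protocol Tables 1 and 2)

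- Window: 18 × 7 = 126 days.
- No-delay schedule, visits 84 days apart: 126/84 = 1.5, so 1 or 2 visits.
- Delayed-start schedule: 1 to 6 visits. The maximum arises, for example, with a transfusion on Day 7. The window runs to Day 7 + 126 = Day 133 and covers Days 14, 28, 42, 56, 84 and 112.

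The six-visit case belongs to delayed starters. Their baseline follows a gap of more than 42 days, about four of the roughly 10-day half-lives in protocol 3.1 (42/10 = 4.2). The on-drug baseline belongs to direct roll-overs. The two should not be combined.

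**3. Shift in mean Hb at a visit**

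Shift = p × d, where p is the share of participants within 18 weeks of a transfusion and d is the mean Hb increment. The documents give neither. Assume p = 5–20% and d = 0.5–2 g/dL.

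- Low: 0.05 × 0.5 = 0.025, about 0.03 g/dL.
- High: 0.20 × 2 = 0.40 g/dL.

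For a given p and d this is an upper bound, because it holds d constant over the whole 18 weeks. For scale only, six adults in the Phase 1b study had a mean rise of 2.3 g/dL (protocol 3.1): 0.025/2.3 = 1% and 0.40/2.3 = 17%.

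**4. VOC**

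If new therapy starts independently of VOCs, covers a share f of person-time and multiplies the rate by RR, the all-data rate changes by f × (RR − 1). With assumed f = 5–30% and RR = 0.5–0.8, this runs from 0.05 × (0.8 − 1) = −1% to 0.30 × (0.5 − 1) = −15%.

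If instead VOCs trigger the therapy, censoring is informative. A simulation used these assumptions: mean 2.5 VOC per year, gamma heterogeneity with dispersion 1, one year of follow-up, and therapy after each VOC with probability q. Without any such therapy the rate was 2.49–2.51.

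| q | Censored (protocol), RR 0.5 / 0.8 | All data (SAP), RR 0.5 / 0.8 |
|---|---|---|
| 0.05 | 2.35 / 2.36 | 2.35 / 2.45 |
| 0.10 | 2.23 / 2.24 | 2.24 / 2.40 |
| 0.20 | 2.06 / 2.05 | 2.09 / 2.32 |

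Here the protocol rule is at least as low as the SAP rule in every row. The direction of the difference therefore depends on why therapy was started.

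**The case against.** **The change is declared and permitted.** Protocol section 10 lets the SAP modify analyses where appropriate and requires an amendment only for major changes to the primary endpoints or their analyses. These are secondary endpoints, nothing is tested, and an all-data summary is a legitimate treatment-policy description. This stands: the all-data summary should stay. It does not supply the missing reason or the missing counts. The estimand that includes all safety data does not supply the reason either, because SAP 3.1.2 takes these four parameters out of the primary laboratory endpoint.

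**Exclusion has its own bias.** If transfusion is given when Hb is falling, dropping the next 18 weeks removes the participants who are doing worst, and the remaining mean is too favorable. Step 4 shows the same for VOC. This also stands. The supplementary summary is a second view and not a correction.

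**Stronger readings that the documents do not support:**

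- *Background therapy is now counted as drug effect.* Stable HU and L-glutamine were never exclusion events, so the SAP changes nothing for them.
- *The SAP flatters the VOC rate.* Step 4 shows that the direction is open. Simple transfusion never censored VOC under either document.
- *The protocol's list misses voxelotor and crizanlizumab.* A reader might infer this because "initiation of new SOC agents (eg, crizanlizumab and voxelotor) during treatment is strongly discouraged", which is softer than a prohibition. Protocol Tables 17 and 18 are partly redacted, are headed as examples and are stated not to be exhaustive, so the inference cannot be checked.
- *The change was driven by results.* The SAP is dated 23 Jun 2025, describes enrollment in the past tense, and the study is open-label. Nothing in the documents shows a motive. The timing only makes a stated reason more useful.

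**Conclusion.** The point holds. SAP 2.1 removes every exclusion and censoring rule in protocol 10.3.3 for these endpoints without a reason, and the SAP contains no analysis under the protocol's rule, no transfusion summary and no count of affected participants. Values after transfusion or new therapy will be mixed into the study's only evidence on hemolytic anemia and cannot be separated from the effect of osivelotor.

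The laboratory parameters carry the finding. The size is unknown. The upper-bound shift of about 0.03–0.4 g/dL in visit-mean Hb rests wholly on the assumed 5–20% and 0.5–2 g/dL. It matters most for direct roll-overs who stay on the same dose; protocol 5.3 and Table 13 allow dose changes, so a near-zero expected change cannot be assumed for everyone. For VOC the loss is one of transparency, with no established direction of bias. This should be fixed, but it does not invalidate the descriptive analyses.

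**What to change.** 1. In SAP 2.1, state why the rules were changed. In 6.2.1 and 6.2.2, label the all-data summaries as treatment-policy and keep them.
2. In 6.2.2, add a supplementary summary of the four laboratory parameters under the protocol 10.3.3 exclusions.
3. Optionally, in 6.2.1, add the VOC analysis under the protocol's censoring, with person-time stopped at the same point.
4. Tabulate by dose arm the participants, visits and person-time affected by each event, with simple and exchange transfusion shown separately.
5. State that exclusion and censoring are informative when transfusion or new therapy follows falling Hb or VOCs, so the two versions are to be read together.

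The cost is SAP wording, one repeat set of existing tables and one count table. Protocol 7.7 already requires concomitant treatments and procedures on the eCRF. Three practical points need settling: whether the eCRF distinguishes simple from exchange transfusion; who decides, before the tables are run, which drugs are known to affect Hb or VOC; and how the imputation of partial medication start dates in SAP 5.4.1.1 affects the classification of HU as new. The number of participants per visit will be smaller in the supplementary summary.

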### 2.2. Study Objectives, Endpoints, and Estimands

The table below has been taken verbatim from the protocol, with change described above.

Presentation of exploratory endpoints maybe modified and are described in the relevant sections (Section 6.3).

Objectives	Endpoints	Estimands
Primary:	Primary:	Primary:
To evaluate the long-term safety of osivelotor in participants with SCD.	
 
• Incidence of TEAEs, changes in laboratory assessments, and changes in vital signs.
 
	The safety estimand for the primary endpoints will consider all safety data collected. Specifically, all data collected on or after obtaining informed consent will be included in the analysis.
Secondary:	Secondary:	Secondary:
To evaluate frequency of VOCs and SCD-related complications.  To evaluate the effects of long-term use of osivelotor on hemolytic anemia.	
 
• Annualized rate of VOC.
 
• Incidence of SCD-related AEs.
 
• Change from baseline in hematological laboratory parameters, including hemoglobin, reticulocytes, lactate dehydrogenase, and unconjugated bilirubin.
 
	Not Applicable

Objectives	Endpoints	Estimands
Exploratory:	Exploratory:	Exploratory:
To evaluate the long-term effects of osivelotor treatment on inflammation, erythropoietin levels, SCD specific biomarkers, and HRQOL assessments.	
 
Change from baseline in adhesion of whole blood to microfluidic channels.
 
Change from baseline in RBC sickling from peripheral blood smears.
 
Change from baseline in RBC deformability and RBC mitochondrial content.
 
Change from baseline in albumin-to-creatinine ratio and kidney injury molecule.
 
Change from baseline in erythropoietin levels.
 
Change from baseline in haptoglobin, hemopexin, and soluble C3.
 
Change from baseline in HRQOL assessments including PROMIS SF Fatigue 13a, PROMIS SF Pain Interference 8a, PROMIS NRS Pain intensity, PGI-C of fatigue and pain, CGI-C of SCD, PGI-S of fatigue and pain, and CGI-S of SCD, EuroQol EQ-5D-5L, and WPAI+CIQ:SCD.
 
	Not Applicable
To evaluate the PK parameters of long-term exposure to osivelotor	Blood and plasma concentrations of osivelotor.	Not Applicable

Abbreviations: CGI-C, Clinician's Global Impression of Change; CGI-S, Clinician's Global Impression of Severity; PGI-C, Patient's Global Impression of Change; PGI-S, Patient's Global Impression of Severity; PK, pharmacokinetic; PROMIS, Patient-Reported Outcome Measurement Information System; HRQOL, health-related quality of life; RBC, red blood cell; SCD, sickle cell disease; SF, short form, WPAI+CIQ:SCD, Work Productivity and Activity Impairment Questionnaire plus Classroom Impairment Questions; Sickle Cell Disease, VOC – vaso-occlusive crisis.

### 2.2.1. Primary Estimand(s)

The safety estimands for the primary endpoints will consider all safety data collected. Specifically, all data collected on or after obtaining informed consent will be included in the analysis.

**Population:** Patients with SCD as defined by the inclusion/exclusion criteria.

**Endpoints:**

- TEAE
- Lab assessments
- Vital Signs

**Intercurrent Events:** NA

**Population Level Summary:** will be provided by group/dose arm (Section 5.3). Specifically,

- for continuous endpoints: Mean
- for categorical endpoints: Proportion

**2.2.2. Secondary Estimand(s)**

Not applicable

**2.2.3. Study Design**

C5351005 (OLE) is designed as a multicenter, global, open-label extension study. The primary objective is to assess the long-term safety of osivelotor in participants with SCD. This study is available to eligible participants who have previously enrolled in a Pfizer-sponsored osivelotor clinical study and meet the entry criteria for this study.

Eligible participants will receive open-label osivelotor at Baseline (Day 1). It is intended that Day 1 coincides with the final visit from the originating osivelotor study. End of Treatment (EOT) assessments from the originating study will serve as Baseline assessments for this study. If Day 1 for this study is greater than 7 days from the completion of the originating study, new baseline assessments will be obtained. If during the period between Day 1 of this study and completion of the originating study no dose is received for greater than 3 consecutive days, an appropriate loading dose will be administered prior to continued maintenance dosing.

Only participants from C5351004 Part A (also referred to as the “parent study”) were enrolled into the OLE. C5351004 Part A is a study which enrolled only adult participants. There are two sets of participants rolling over from C5351004 Part A to the OLE study – (i) participants without a delayed start (Date of first dose in C5351005 – EOT date from C5351004 + 1 ≤ 42 days) and (ii) participants with a delayed start of OLE (Date of first dose in C5351005 – EOT date from C5351004 + 1 > 42 days). Each set follows a distinct schedule of assessments as outlined in the C5351005 protocol.

**3. ENDPOINTS AND BASELINE VARIABLES: DEFINITIONS AND CONVENTIONS****3.1. Primary Endpoint(s)****3.1.1. Incidence of TEAEs**

A treatment-emergent adverse event (TEAE) is defined as an AE that occurs during the effective duration of treatment defined as the time from the first dose of study drug through last dose of study drug + 56 days.

TEAEs that occur in the parent study are not counted as TEAEs in this study. In case, the start date of AE is the same date as the treatment start date and the question in the AE CRF page “Is this AE continuing from the parent study?” = “Yes”, then the event is not a TEAE,

as long as it can be confirmed that the AE in question had a start date in the parent study and no end date in the parent study.

In addition, in case the start date of AE is unknown (partially or fully unknown) and the response to the question in AE CRF page “If complete date is not known or the start date is the same as Day 1, did the AE start prior to dosing?” = “No”, then the event is a TEAE. This particular CRF question will only be used when the AE start date is not completely known or the start date is the same as Day 1.

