Participants will be followed for approximately 12 weeks after completing dosing to further assess safety. Participants should return to the study site for an EOS visit approximately 12 weeks after the last dose of study drug.

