#### **9.4.6. Adverse Event Reporting**

##### **9.4.6.1. General AE Reporting**

All AEs/SAEs will be recorded from the time the study participant/parent/legal guardian/legally authorized representative signs the ICF/assent form until the EOS Visit or ET Visit, whichever comes first. The AE or SAE must be recorded on the CRF and the SAE reported using PSSA. The Investigator is responsible for evaluating all AEs/SAEs, obtaining supporting documents, and ensuring that documentation of the event is complete. Details of each reported AE/SAE must include at a minimum severity, relationship to study treatment, duration, and outcome.

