##### **9.4.7. Time Period and Frequency for Collecting AE and SAE Information**

The time period for actively eliciting and collecting AEs and SAEs ("active collection period") for each participant begins from the time the participant/parent/legal guardian/legally authorized representative provides informed consent, which is obtained before undergoing any study related procedure and/or receiving study intervention, through and including a minimum of 63 calendar days after the last administration of the study intervention. Follow-up by the investigator continues throughout the active collection period and until the AE or SAE or its sequelae resolve or stabilize at a level acceptable to the investigator.

When a clinically important AE remains ongoing at the end of the active collection period, follow-up by the investigator continues until the AE or SAE or its sequelae resolve or stabilize at a level acceptable to the investigator and Pfizer concurs with that assessment.

For participants who are screen failures, the active collection period ends when screen failure status is determined.

If the participant withdraws from the study and also withdraws consent for the collection of future information, the active collection period ends when consent is withdrawn.

If a participant permanently discontinues or temporarily discontinues study intervention because of an AE or SAE, the AE or SAE must be recorded on the CRF and the SAE reported using PSSA Pfizer's Serious Adverse Event Submission Assistant. The Sponsor/Medical Monitor(s) must be notified of the study participant discontinuation.

Investigators are not obligated to actively seek information on AEs or SAEs after the participant has concluded study participation. However, if the investigator learns of any SAE, including a death, at any time after a participant has concluded study participation, and they consider the event to be reasonably related to the study intervention, the investigator must promptly report the SAE to Pfizer using PSSA.

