## 6. ANALYSES AND SUMMARIES

### 6.1 Primary Endpoint(s)

The safety estimand for the primary endpoints will consider all safety data collected. Specifically, all data collected on or after obtaining informed consent will be included in the analysis.

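### AEs starting more than 56 days after last dose enter no incidence table although the SAP says all safety data collected will be analysed, and the two protocol rules for ending AE recording disagree for early terminators

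*SAP*

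**What the plan says.** **TEAE window.** SAP 3.1.1 defines the window as "the time from the first dose of study drug through last dose of study drug + 56 days". SAP 5.1 takes the date of last dose from the EOT eCRF page. The protocol gives no TEAE window of its own.

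**AE collection.** Protocol 9.4.7 runs active collection from consent through "a minimum of 63 calendar days after the last administration of the study intervention". Protocol 9.4.6.1 records AEs "until the EOS Visit or ET Visit, whichever comes first". Protocol 5.1 places EOS about 12 weeks after last dose and gives the purpose: "Participants will be followed for approximately 12 weeks after completing dosing to further assess safety".

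**Stated scope of the analysis.** SAP 6.1, directly above the AE analysis, says "all data collected on or after obtaining informed consent will be included in the analysis". SAP 2.2.1 says the same for the primary estimand.

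**What is tabulated.** The overall incidence table and all the SOC/PT tables in SAP 6.1.1 are TEAE tables, and the SCD-related AE tables in SAP 6.2.3 are limited to treatment-emergent events. Other AEs appear in a listing of all AEs, with deaths listed separately. Unless otherwise specified, percentages use the header N as denominator (SAP 5.3.1).

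**The concern.** The study's primary objective is long-term safety, and the post-treatment visit exists to assess safety further. An SAE with a known onset 60 days after last dose falls inside the mandatory collection period, yet it contributes to no count or percentage. A reader of the primary safety tables would not see it, and the estimand text would lead that reader to believe it had been included.

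The second issue is how much of the window is observed. If an ET visit soon after last dose ends AE recording, no new onsets are recorded for the rest of that participant's TEAE window. The participant still counts in full in the denominator, so incidence is understated to an unknown degree.

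**Working it through.** There is no planned figure to reproduce. The check compares the time limits and then follows events through the tables.

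**Inputs.** TEAE cutoff 56 days (SAP 3.1.1); minimum active collection 63 days (Protocol 9.4.7); EOS about 12 weeks, or 12 × 7 = 84 days (Protocol 5.1); half-life in SCD about 10 days (Protocol 3.1). All days below are counted from last dose.

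**Collected time outside the TEAE window**
- Against the 63-day minimum: 63 − 56 = 7 days; 7/63 = 11.1%.
- Against EOS: 84 − 56 = 28 days; 28/84 = 33.3%.

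These are shares of post-dose time. As a share of all observation time they depend on treatment length:
- 252 treatment days (Protocol synopsis) plus 84 gives 336 days: 7/336 = 2.1%, 28/336 = 8.3%.
- Treatment to Week 84 (588 days, a visit in the SAP Appendix 1.1 windows) plus 84 gives 672 days: 7/672 = 1.0%, 28/672 = 4.2%.

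**Possible number of events.** The documents give no AE rate, so a range of 0.5 to 5 new AEs per participant-year is assumed. Expected AEs outside the window per 100 participants followed = 100 × rate × gap/365.25.

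| Assumed rate | 7-day gap | 28-day gap |
|---|---|---|
| 0.5 | 1.0 | 3.8 |
| 1 | 1.9 | 7.7 |
| 3 | 5.7 | 23.0 |
| 5 | 9.6 | 38.3 |

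**Is 56 days unreasonable in itself?** At a 10-day half-life, 56, 63 and 84 days are 5.6, 6.3 and 8.4 half-lives. The fraction remaining, 0.5^(days/10), is 2.06%, 1.27% and 0.30%. Pharmacology does not separate 56 from 63. The SAP gives no reason for 56, and SAP 2.1 does not mention the window.

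**Is the cutoff applied evenly?** No. Under SAP 3.1.1, an AE with a partial or unknown start date is a TEAE if the CRF says it did not begin before dosing. No check against last dose + 56 days follows, and SAP 5.4.1.4 imputes no start dates. An AE starting on post-dose day 70 is excluded if its date is complete and can be counted if it is not.

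**Early terminators.** Protocol 8.3 holds the early discontinuation visit when the participant leaves the study. Let that visit fall t days after last dose:
- t below 63: Protocol 9.4.6.1 ends recording at t, while 9.4.7 still requires 63 days. The sections contradict each other.
- t below 56: 56 − t days of the TEAE window are also unobserved for new onsets. For example, t = 7 (assumed) leaves 49 of 56 days unobserved.
- t of 63 or more, including EOS at about 84: the two sections are compatible.

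**The case against.** A reader might infer that all these time limits conflict. They do not. A 56-day TEAE definition inside a minimum 63-day collection period inside an 84-day follow-up is a nested arrangement, and a TEAE window shorter than collection is not an error by itself. The only direct clash between time rules is Protocol 9.4.6.1 against 9.4.7 when the ET visit falls before day 63.

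A reader might also infer that late events are discarded. They stay in the AE and death listings, and some with incomplete dates can reach the tables. Two of the three primary endpoints, laboratory values and vital signs, have no last-dose cutoff in the SAP visit windows.

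The estimand's endpoint is named as the TEAE, and in Protocol 10.1.1 the all-data sentence sits under intercurrent events, where it can be read as dropping nothing because of such events. That is a fair reading of the protocol. It is harder to sustain for SAP 2.2.1 and 6.1, which state without qualification that all safety data collected are considered.

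On early leavers, it is tempting to say they are the people most likely to have had safety problems. The documents give no data for that. Stopping drug alone does not end follow-up, since Protocol 8.2 sends these participants to the 12-week EOS visit. Those withdrawn for an AE are followed until its outcome is determined (Protocol 8.2.2), although following a known AE does not capture new ones. Withdrawal of consent for future information properly ends collection under 9.4.7.

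Finally, 56 days is as defensible as 63, so insisting on 63 would be preference.

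**Conclusion.** The concern holds in a limited form. AEs with a known onset after day 56 are outside every incidence table, although the SAP's stated scope includes them. The gap is 7 days against the collection minimum and about 28 days against EOS. On the assumed rates, the 28-day gap would leave about 4 to 38 AEs per 100 participants followed to EOS out of the tables; the true number cannot be derived from the documents. The day counts assume EOS at about 84 days.

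Separately, the protocol contradicts itself on when AE recording ends for anyone with an ET visit before day 63, and the TEAE window is only partly observed when that visit precedes day 56. How many participants this affects is not known.

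The consequence is descriptive completeness of the primary safety endpoint. No hypothesis is tested, so no error rate or sample size is affected. The change is worth making because it is cheap and alters what the report shows.

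**What to change.** 1. **SAP 6.1.1:** add one summary table of AEs, SAEs and deaths with onset after the TEAE window through EOS. This meets the stated scope whichever cutoff is used.
2. **SAP 3.1.1, 2.2.1 and 6.1:** either align the TEAE window with the 63-day collection period, or keep 56 days, state the reason, and limit the estimand wording to match.
3. **SAP 3.1.1:** apply the same upper bound to AEs with partial start dates wherever the known parts of the date allow it.
4. **Protocol 9.4.6.1 and 9.4.7:** reconcile them so that recording runs to at least 63 days after last dose unless consent for future data is withdrawn. The SAP is dated June 2025 and describes enrolment in the past tense, so new wording cannot recover data from participants who have already terminated. For them, report how many had follow-up shorter than the TEAE window.

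The cost is one table, a follow-up count, a few sentences in the SAP and one prospective protocol clarification. TEAE counts may rise slightly if the window moves to 63 days, and may fall slightly once the upper bound applies to partial dates.
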